# G. Study Subjects

In order to be included in this study, the patient must meet the following inclusion criteria:

- 1) Have documentation of HIV-1 positive status
- 2) Have a positive score on the Drug Abuse Screening Test (DAST)
- 3) Use cocaine regularly and more often than any other drug or alcohol
- 4) Express an interest in stopping their cocaine use
- 5) Must not be currently taking antiretroviral therapy
- 6) Have a viral load >55,000 copies/ml and a CD4 count < 200; thereby placing the subject in a category that should definitely receive therapy according to national guidelines [8b]. Treatment at higher CD4 loads and lower viral loads has still not been shown to affect clinical outcomes of time to disease progression and given the likelihood of non-adherence in drug-abusing populations is higher than in the general population, it may be unethical to start people on HAART when there are uncertain recommendations at present.

If a subject meets any of the following exclusion criteria, they will not be allowed to participate in the study:

- 1) On any form of antiretroviral therapy within the 4 months prior to the study
- 2) Exhibiting signs of physical dependence on any drug other than cocaine
- 3) Living in a facility where medicines are dispensed for them
- 4) Unable to give informed consent

Subject participation will not be limited on the basis of gender or race. Based on population of the community in which the study is to take place, Caucasian, Latino and African-American subjects will be primarily recruited. It is likely that slightly more men will be included in men as there are a larger proportion of male drug abusers in the general population.

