The primary outcome variable is percentage of total prescribed medication doses taken as assessed by a 3 day self-report adherence questionnaire. The percentage of total prescribed doses taken will be compared in the two arms with a  $X^2$  test. Prior studies of non-drug abusers have shown that most patients report approximately a 70-80% adherence rate over the week prior to questioning with a standard deviation of around 20[8]. This self-reported adherence rate correlates with an actual adherence rate of around 55% as measured by microelectronic monitoring systems [8]. In other words, patients usually over report adherence by approximately 15-20% in a reproducible manner that still predicts changes in viral load. There is little data looking at self-reported adherence in a drug abusing population. One study has shown however that 32% of drug users obtain a viral load <400 copies/ml compared to 45% of non-users. The approximately 45% virologic response in non-users in this study is similar to the electronically monitored compliance of 55% in the previous study [7]. The lessened virologic response may be a result of pharmocokinetics and pharmocodynamics as well as viral resistance. Therefore, based on prior studies, non-users of drugs are likely to self-report around 70% adherence. Given, the lack of significant data on active drug abusers, 50% self-reported adherence is a reasonable estimate. To detect this difference, 17 subjects in each group are required.

To detect a  $0.9 \log_{10}$  difference in change in HIV-1 RNA viral load at 8 weeks (the time interval it takes to detect a  $1 \log_{10}$  change in viral load according to national guidelines) between groups assuming a standard deviation of 1.5 by unpaired t-test, a sample size of 45 subjects in each arm is required. Change in viral load is defined as the difference in  $\log_{10}$  copies/ml between the value measured at the time of the initial visit and the value at the 8-week visit. In a study comparing drug users and non-users, a  $0.9 \log_{10}$  difference was detected ( $0.8 \log_{10}$  change in the drug users and a  $1.7 \log_{10}$  change in the non-users) [7].

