#### C. Study Procedure

All subjects participating in the study are to be followed by medical care providers in the outpatient HIV clinic and all medical management will be left to the discretion of those providers. The time intervals chosen in this study for checking viral loads after the initiation of HAART therapy correspond with national treatment guidelines [9]; however additional blood tests are at the discretion of the medical provider. Although it is not possible to blind this study, no data will be shared with either the subjects or their providers. The study period will last 4 months. Study visits will occur once a week for the first 6 weeks and then every 2 weeks thereafter. Subjects in both arms will have a urine dip test to

Columbia University College of Physicians and Surgeons

check for cocaine at every visit which will only take 5 minutes to collect and process. Also, every two weeks the subjects will be asked the questions on the 3-day adherence questionnaire to assess their medication adherence. The questionnaire will take about 15 minutes at these visits. The urine samples and questionnaires will be completed with an investigator in the HIV outpatient clinic prior to any medical visit that subject might have that day. The subjects in the treatment arm will have therapy sessions in the addiction medicine research clinic on the same days as their other study activities. All subjects will receive compensation for coming to the scheduled visits and providing urine samples in the form of vouchers. They will receive a \$15 voucher at each visit in the form of subway fare (Metrocard) or a voucher to a local fast food chain. If they complete the study and come to all of the scheduled visits, they will receive a \$50 gift certificate to Old Navy.

At the first visit, informed consent will be obtained and the study will be explained to the patient by one of the investigators. Also, the primary medical provider will initiate HAART therapy. Because adherence to the prescribed regimen is the primary outcome, patients may be placed on any of the "strongly recommended" regimens according to current national guidelines [9] at the discretion of the primary medical provider as long is the regimen is a class sparing regimen. (e.g. NNRTI-sparing, PIsparing or a PI- and NNRTI-sparing regimen) The medical care provider will choose a regimen at the first study visit while still blinded to which arm of the study the patient is in to avoid biasing the choice.

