#### H. Recruitment of Subjects

Subjects will be recruited at New York Presbyterian Hospital's Columbia Presbyterian Medical Center over a two-year period in both the outpatient HIV clinic as well as in the inpatient setting. All patients who present to the HIV clinic or the inpatient service for treatment of HIV or HIV-related diseases will be screened with the Drug Abuse Screening Test (DAST). If it is positive, the patient would like help with their drug abuse and the patient's primary drug of abuse is cocaine, they will be recruited to participate in the study.

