The score is equal to the number of questions you answered **Yes** A score of 5 or less points indicates a Normal Score. A score of 6 or more points indicates a Drug Problem.

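### No planned analysis uses the pre-randomisation DAST total, and the primary comparison is an unadjusted chi-square test; the cost is a modest loss of precision

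*Protocol*

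**What the plan says.** **Use of the DAST.** Under Protocol section H, patients presenting for HIV care "will be screened with the Drug Abuse Screening Test (DAST"); recruitment, consent and randomisation follow. Section G, inclusion criterion 2, requires that the patient "Have a positive score on the Drug Abuse Screening Test (DAST"). The appended form has 28 Yes/No items, scored as the number of Yes answers, and states: "A score of 6 or more points indicates a Drug Problem". The total is not used to stratify the envelope draw, and no analysis names it.

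**Baseline adherence.** There can be none. Section G requires that a subject "Must not be currently taking antiretroviral therapy" and excludes anyone "On any form of antiretroviral therapy within the 4 months prior to the study". Section C says of the first visit: "Also, the primary medical provider will initiate HAART therapy".

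**Primary analysis.** Section B: "The primary outcome variable is percentage of total prescribed medication doses taken as assessed by a 3 day self-report adherence questionnaire". Then: "The percentage of total prescribed doses taken will be compared in the two arms with a" chi-square test. No covariate is mentioned.

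**Regression.** Section B also plans a multiple linear regression of adherence on age, gender, ethnicity, the share of on-study urines positive for cocaine, use of other treatments, and further predictors known from the literature. Neither arm nor the DAST is named.

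**The concern.** The trial's premise, in section A, is that active drug use lowers adherence. If so, the extent of a subject's drug problem at entry is a natural candidate to explain differences in adherence between subjects. The usual best covariate, a baseline value of the outcome, cannot exist here, so other baseline information matters more. The DAST total is already obtained on everyone before randomisation, yet neither planned analysis uses it.

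The regression does not fill the gap. As written it is not a treatment comparison, because arm is not in it. Its one cocaine measure is taken during the study and is something the therapy is meant to change. If arm were added alongside it, part of any treatment effect could be adjusted away.

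At stake is precision: variation in adherence that is linked to initial severity stays in the error term, and a chance imbalance in severity is not corrected.

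**Working it through.** **Inputs from the protocol (section B):** expected adherence 70% v 50%, a difference of 20 points; SD about 20; 17 per group stated as required for the primary outcome; 182 enrolled, so 91 per arm, a number set by the viral-suppression outcome.

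**Assumed:** two-sided alpha 0.05 and 80% power, since neither is stated; a correlation ρ between DAST total and a subject's adherence percentage, which the protocol does not give, shown from 0.1 to 0.5; and all 91 per arm contributing data.

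**Step 1: reproduce the stated size.** Comparison of two means, normal approximation:

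n per arm = 2 × (1.96 + 0.8416)² × (20/20)² = 15.7, rounded up to 16.

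The t-test version gives 16.7, i.e. 17, as stated, and 17 per arm has 80.7% power. Treating 70% v 50% as two proportions would need 93 per arm (103 with continuity correction). The 17 is therefore a calculation for means, and a linear model fits it.

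**Step 2: effect of adjustment.** Adjusting for a covariate with correlation ρ reduces the SD to 20 × √(1 − ρ²). The difference detectable with 80% power at 91 per arm is

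(1.96 + 0.8416) × SD × √(2/91), with √(2/91) = 0.1483.

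| ρ (assumed) | Residual SD | Detectable difference (points) | Power for 8 points |
|---|---|---|---|
| 0 (unadjusted) | 20.00 | 8.31 | 77.0% |
| 0.1 | 19.90 | 8.27 | 77.4% |
| 0.3 | 19.08 | 7.92 | 80.7% |
| 0.5 | 17.32 | 7.19 | 87.6% |

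The gain is between 0.04 and about 1.1 points. For the planned 20 points, unadjusted power at 91 per arm already exceeds 99.99%.

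**Step 3: the same gain in subjects.** Equivalent extra subjects = N/(1 − ρ²) − N. At ρ = 0.2, 0.3 and 0.4:

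- N = 182: 7.6, 18.0 and 34.7.
- N = 34 (17 per group, the stated need for the primary outcome): 1.4, 3.4 and 6.5.

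**Step 4: chance imbalance.** The difference in mean DAST between arms has a 95% range of ±1.96 × 0.1483 = ±0.29 SD. The matching shift in the adherence difference is 0.29 × ρ × 20, or about 0.6, 1.7 and 2.9 points at ρ = 0.1, 0.3 and 0.5.

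**The case against.** **Covariates are a matter for the SAP.** Often they are, and the SAP is not shown. But this protocol itself fixes the primary test and names regression covariates. A chi-square test of the two arms cannot carry a continuous covariate, so the choice has been made here. It is true that the regression list is open-ended and could admit the DAST. Without arm in the model, that would still not sharpen the treatment comparison.

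**The DAST cut-off is not why the test is unadjusted.** This stands. A reader might infer that using the score as pass/fail forces an unadjusted analysis. It does not: the choice of chi-square does, and age, gender, ethnicity, viral load and CD4 count could also serve as covariates. Nor do the documents say that the total is discarded; section I keeps questionnaire data under each subject's code.

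**The DAST may be a weak predictor.** This stands too. Section F supports it as a screening tool at the cut-off of 6. It covers drugs in general, many items ask about lifetime events, and the entry criteria may narrow its range. The form counts every Yes, although on item 4 (managing a week without drugs) and item 5 (always able to stop) a Yes suggests fewer problems. A cocaine urine result from the first visit might be another baseline marker, but whether that sample precedes randomisation is not stated.

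**The trial has ample power.** For 20 points, yes. However, section B takes that figure from non-users against active users, whereas the trial compares users given therapy with users given referrals. A smaller effect is plausible, and near 8 points precision counts.

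**Conclusion.** The point holds as a minor improvement in efficiency. The protocol fixes an unadjusted primary comparison and a regression without arm, and neither uses the one drug-problem scale scored on every subject before randomisation.

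A reader might go further and infer that the primary result is biased or in danger. The documents do not support that. Randomisation keeps the unadjusted comparison unbiased, its standard error already allows for chance imbalance, and power for the planned effect is not materially changed by adjustment. The gain is a reduction in the detectable difference from 8.31 points to between 8.27 and 7.19. It rests on an assumed correlation of 0.1 to 0.5 and on the protocol's SD of 20. If the correlation is near zero, there is nothing to gain and almost nothing to lose.

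**What to change.** In section B, replace the chi-square test of the primary outcome with a linear model of each subject's adherence percentage containing arm and the pre-randomisation DAST total, named in advance as a covariate. State that the total, and not only the pass/fail result, is kept as a baseline variable. Before it is used, check the keying of items 4 and 5 on the appended form against the source instrument. State that on-study urine results do not enter this arm comparison; they can remain in the separate descriptive regression.

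No new data are needed. The cost is one degree of freedom and a change of primary test, which is more than a wording edit but agrees with the means-and-SD basis on which the 17 per group was calculated.

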# Cognitive behavioral therapy for cocaine addiction to improve antiretroviral medication adherence in HIVpositive patients

# [name]

# A. Study Purpose and Rational

Many research studies have revealed that highly active antiretroviral therapy (HAART) improves HIV-related clinical outcomes, such as decreased opportunistic infections and prolonged survival as well as improves surrogate markers such as HIV viral load and CD4 cell counts [1,2]. Furthermore, optimal adherence to HAART regimens is necessary to obtain adequate viral suppression [3-5] and to avoid the emergence of viral resistance [6]. Patients who are actively abusing illicit drugs, including cocaine, have been shown to demonstrate decreased adherence to HAART as well as inferior virologic and immunologic responses to therapy as compared to both former and non-drug users [7]. Therefore, it is likely that helping these patients eliminate their illicit drug use may improve their adherence to HAART and their HIV clinical outcomes. The purpose of this study is to show that providing active cocaine abusers with cognitive behavioral therapy aimed at relapse prevention and coping skills training will increase their HAART regimen medication adherence as assessed by a self-adherence questionnaire over a 4 month period.

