# The Drug Abuse Screening Test (DAST)

For each question below, please circle either a Yes or No

1.	Have you used drugs other than those required for medical reasons?	Yes or No
2.	Have you abused prescription drugs?	Yes or No
3.	Do you abuse more than one drug at a time?	Yes or No
4.	Can you get through the week without using drugs (other than those required for medical reasons)?	Yes or No
5.	Are you always able to stop using drugs when you want to?	Yes or No
6.	Do you abuse drugs on a continuous basis?	Yes or No
7.	Do you try to limit your drug use to certain situations?	Yes or No
8.	Have you had "blackouts" or "flashbacks" as a result of drug use?	Yes or No
9.	Do you ever feel bad about your drug abuse?	Yes or No
10.	Does your spouse (or parents) ever complain about your involvement with drugs?	Yes or No
11.	Do your friends or relatives know or suspect you abuse drugs?	Yes or No
12.	Has drug abuse ever created problems between you and your spouse?	Yes or No
13.	Has any family member ever sought help for problems related to drug use?	Yes or No
14.	Have you ever lost friends because of your use of drugs?	Yes or No
15.	Have you ever neglected your family or missed work because of your use of drugs?	Yes or No
16.	Have you ever been in trouble at work because of drug abuse?	Yes or No
17.	Have you ever lost a job because of drug abuse?	Yes or No
18.	Have you gotten into fights when under the influence of drugs?	Yes or No
19.	Have you ever been arrested because of unusual behavior while under the influence of drugs?	Yes or No
20.	Have you ever been arrested for driving while under the influence of drugs?	Yes or No
21.	Have you engaged in illegal activities in order to obtain drugs?	Yes or No
22.	Have you been arrested for possession of dangerous drugs?	Yes or No
23.	Have you ever experienced withdrawal symptoms as a result of heavy drug intake?	Yes or No
24.	Have you had medical problems as a result of your drug use (e.g., memory loss, hepatitis, convulsions, bleeding, etc.)?	Yes or No
25.	Have you ever gone to anyone for help for a drug problem?	Yes or No
26.	Have you ever been in a hospital for medical problems related to drug use?	Yes or No
27.	Have you ever been involved in a treatment program specifically related to drug care?	Yes or No
28.	Have you been treated as an out-patient for problems related to drug use?	Yes or No

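### Cocaine use at entry is established only by self-report, and no urine result from before randomisation is designated as baseline or used in the arm comparisons, although a dip is planned at every visit

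*Protocol*

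**What the plan says.** Section A sets the aim as "providing active cocaine abusers with cognitive behavioral therapy aimed at relapse prevention and coping skills training" in order to raise adherence. It also says that active drug users have lower adherence and poorer virologic and immunologic responses than former users and non-users.

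Cocaine status at entry rests on three of the inclusion criteria in section G: a positive DAST, the requirement to "Use cocaine regularly and more often than any other drug or alcohol", and to "Express an interest in stopping their cocaine use". Section H describes recruitment the same way: the DAST is given, and "If it is positive, the patient would like help with their drug abuse and the patient's primary drug of abuse is cocaine", the patient is approached. Recruitment takes place "in both the outpatient HIV clinic as well as in the inpatient setting". No urine result, interview, frequency or look-back period is named.

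The DAST in the appendix has 28 items about drugs in general, for example "Have you ever lost friends because of your use of drugs". The score is the number of Yes answers, and 6 or more is positive.

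Section C has subjects in both arms take a urine test to "check for cocaine at every visit which will only take 5 minutes to collect and process". Allocation in section B is from one box of sealed envelopes, half for each arm. The arm comparisons named there are a chi-squared test for adherence, an unpaired t-test for change in log10 viral load and a chi-squared test for undetectable viral load. Urine appears only in a separate multiple regression for adherence, as the percentage of positive samples during the study.

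**The concern.** HIV status, viral load and CD4 count at entry are documented or measured. The exposure that the therapy is meant to change is taken on the subject's word, with regular use left undefined. By section A's own premise, active use predicts both adherence and viral response, so cocaine status at entry is a natural baseline variable.

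The only urine variable in the analysis cannot serve as that baseline. The percentage positive over the study is measured mostly or wholly after allocation and lies on the path from therapy to adherence. Adjusting an arm comparison for it would remove part of the effect being sought. As written, the trial could finish with no designated objective measure of cocaine use before treatment, neither to describe the population nor to adjust for chance differences between arms.

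**Working it through.** **1. What the DAST can establish.** Item count from the appendix:
- Lifetime or undated past: items 1, 2, 8 and 12 to 28, so 3 + 17 = 20 of 28 (71%). Of these, 12 use the word ever (12-17, 19, 20, 23, 25-27) and 8 carry no date (1, 2, 8, 18, 21, 22, 24, 28).
- Present tense: items 3-7 and 9-11, so 8 of 28.
- Items naming cocaine: none.

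The cut-off of 6 can therefore be reached on past use of any drug. Current cocaine use is carried by criterion 3 alone.

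**2. Is there a dip before allocation?** Section C says every visit, which includes the first. Section B, for the standard-of-care arm, ties the urine sample to visits mentioned just after the return schedule. The first-visit paragraph of section C lists consent and the start of HAART, but no dip. A first-visit dip is a fair reading, but its timing relative to the envelope is not fixed.

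**3. The plan's own sample size.** Inputs from section B: 40% v 20% undetectable, 91 per arm. Alpha and power are not stated; two-sided 0.05 and 80% are assumed.
- Uncorrected: n = [1.96 × √(2 × 0.30 × 0.70) + 0.842 × √(0.24 + 0.16)]² / 0.20² = 81.2, so 82.
- With continuity correction: (81.2/4) × [1 + √(1 + 4/(81.2 × 0.20))]² = 90.9, so 91. The stated figure is reproduced.

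**4. Chance imbalance in a baseline dip.** Assumption: 50% positive (the documents give no rate).
- SD of the between-arm difference = √(2 × 0.25/91) = 0.074, or 7.4 points.
- P(gap of 10 points or more) = P(|Z| > 0.10/0.074 = 1.35) = about 0.18.

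**5. What a 10-point gap is worth.** Section B's contrasts between users and non-users are 50% v 70% adherence, 32% v 45% suppressed, and 0.8 v 1.7 log10 change.
- Adherence: 0.10 × 20 = 2 points. Taking SD 20, the standard error of the arm difference is 20 × √(2/91) = 3.0 points.
- Suppression: 0.10 × 13 = 1.3 points. The standard error is √(0.40/91) = 6.6 points.
- Log10 change: 0.10 × 0.9 = 0.09. The standard error is 1.5 × √(2/91) = 0.22.

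These shifts assume that one dip separates subjects as sharply as the user/non-user contrast does. That is generous among people who all report regular use.

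**6. Dilution, as illustration only.** Suppose a share q of entrants are not using and gain nothing, with the control rate kept at 20%. Power is at 91 per arm, continuity-corrected for suppression.

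| q | Suppression rates | Power | n per arm for 80% | Power, log10 change |
|---|---|---|---|---|
| 0 | 40% v 20% | 80% | 91 | 98% |
| 10% | 38% v 20% | 71% | 110 | 95% |
| 20% | 36% v 20% | 61% | 135 | 90% |
| 30% | 34% v 20% | 50% | 171 | 81% |

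The adherence comparison, treated as means with SD 20, keeps over 99% power throughout. The documents give no value for q.

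**The case against.** The strongest reply is that the entry criteria are cumulative. A reader might infer from the DAST count that former users, or users of another drug, qualify. They do not: a DAST of 6 built on past use still fails criterion 3, which requires current regular use with cocaine predominant, and section H repeats that cocaine must be the primary drug. Current use is required in words; only its definition and verification are missing.

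A reader might also infer that the trial is materially diluted or underpowered. The documents do not support this. They give no share of non-users, and zero benefit for such subjects sits badly with a therapy aimed at relapse prevention, for which section C cites more durable cessation attempts and less severe relapses. Nothing shows that the $15 visit vouchers or the $50 completion gift draw in ineligible people. The primary comparison would keep ample power anyway.

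Nor is a chance imbalance a bias. Randomisation covers it through the test's error rate, and unstratified allocation of 182 subjects is acceptable. A single dip does not measure a pattern of use either: one negative result does not show non-use, least of all in an inpatient whose use admission may have interrupted.

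Finally, covariates are often left to a statistical analysis plan, which is not at hand. That is fair for the model's details. The order of the dip and the envelope is a matter for the protocol, however, and cannot be recovered later. All of these limits stand. None of them supplies a baseline measure.

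**Conclusion.** The point holds as an inexpensive improvement, not as an error in the plan. Cocaine use at entry is self-reported, no pre-allocation urine result is designated as baseline, the arm comparisons named are unadjusted, and the one urine variable in the analysis is post-randomisation and unfit as a baseline.

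The size is modest. Assuming 50% positive at entry, a gap of 10 points or more arises in about 18% of trials and moves the outcomes by about 1 to 2 percentage points, or 0.09 log10, at section B's contrasts. Adjustment should also improve precision somewhat. By how much depends on how well one dip predicts outcome in this population, which the documents do not say. The dilution figures rest on assumed rates and bear mainly on the secondary suppression endpoint.

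Two stronger conclusions are tempting and should not be drawn. One is that a first-visit result is already in hand and being wasted: the dip is implied, not explicit. The other is that entry must be limited to subjects with a positive dip: that would change the target population and is a trade-off for the sponsor.

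**What to change.** In section C, state that the first-visit dip is done after consent and before the envelope is drawn, and that its result is recorded as baseline cocaine status. Section C already has the provider choose the regimen at that visit before knowing the arm, so a step before allocation fits the visit.

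In section B, keep this result separate from the percentage of positive samples during the study, and make it a prespecified covariate in the arm comparisons. For example, use linear regression for each subject's percentage adherence and for log10 viral load change, and logistic regression for undetectable viral load. The adjusted odds ratio is conditional on baseline status, so the two raw proportions should be reported beside it.

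The cost is reordering a planned 5-minute test and one covariate. If the plan does not in fact include a first-visit dip, the cost is one extra dip per subject.

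Optional, for the sponsor to weigh:
- Give criterion 3 a look-back window and a definition of regular use.
- Use separate envelope sets by dip result. These need blocking within each set, because stratum sizes are unknown in advance and the single half-and-half box would no longer keep the arms equal.
- Require a positive dip for entry, with a repeat allowed, at the price of losing some intermittent users.
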